11. ETHICAL CONSIDERATIONS

The study protocol and forms will be submitted to the UCSF Committee on Human Research, as well as the Scientific and Ethical Review Unit (SERU) of the Kenya Medical Research Institute (KEMRI). No aspect of the study will be conducted without explicit study approval from both UCSF CHR And KEMRI SERU.

(a) Human Subjects**(a1) "First, do no harm."**

The primary risks associated with the study are loss of confidentiality and risks to reputation. Participation in this research and research results will be kept as confidential as possible. No individual identities will be used in any reports or publications resulting from the study.

There is also the risk of fatigue from interviewing or participation in the group discussion. In addition, participants will be asked some sensitive questions regarding mental health, which may lead to personal discomfort or embarrassment. Participants are free to decline to answer any questions and can stop the interview or leave the discussion at any time. Field staff will be trained in non-judgmental interactions, how to recognize and respond to any distress and strategies designed to minimize these risks and their potential impact on study participants. To avoid fatigue, interviews and discussions will be kept to no more than 2 hours, with breaks available as needed. All serious and unexpected adverse events will be reported to the Study PIs and to the relevant IRBs per local regulation. We have preemptively come up with a number of procedures to protect study participants against any potential risks that may result from study participation, including:

Planned procedures for protecting against fatigue: Interviews as well as focus group discussions will last 1-2 hours. Participants will be informed that they can take a break or stop at any time. Staff will be well-trained and supervised under the direction of experienced clinical researchers.

Planned procedure for protection of risks due to sensitive questions: Efforts will be made to minimize discomfort by assuring that interviewers and discussion moderators are well trained and that they will inform participants beforehand about the nature of the questions and assure participants of privacy.

For the In-Depth Interviews: The interviewer will be available after the interview to debrief the participant if s/he is in any way concerned by the nature of the questions. Routine demographic questions will be asked first, followed by more personal questions. Participants will be informed that they have the right to decline participation in the study, to refuse to answer any questions, or to withdraw at any time without adverse consequences. Sensitive questions such as sexual risk may be asked using ACASI. Since the Ministry of Health with additional support from implementing partners such as the FACES program provides comprehensive AIDS education, counseling, and services, it will be possible for the interviewers to provide immediate referrals for research participants who are in emotional distress or exhibit any concerning physical signs or symptoms. As we will screen for depression, for participants who have suicidal thoughts, we will ask participants to speak with one of our study health providers who can further screen them for suicidal ideation and make appropriate referrals if they are suicidal. This may lead to some discomfort, but we hope will provide benefits for the participants if they are able to get access to appropriate mental health care.

For the Focus Group Discussions: ***Disclosure of HIV status to other focus group participants by virtue of participating in the group.*** Potential negative effects associated with this risk are minimized through our IRB-approved recruitment procedures and informed consent that clearly conveys to individuals that they will be identified as being HIV positive through participation in the focus group. Participants are informed of this risk, however cannot be fully protected from it. However, women attending PMTCT care are already unofficially disclosing their status by virtue of PMTCT counseling addressing HIV positive women. This does not lessen the impact of the potential risk, however, it speaks to women attending PMTCT are in essence self-disclosing to their peers already.

Potential for others in focus group to fail in maintaining participant's privacy. We cannot guarantee everyone will honor the pledge of confidentiality and therefore this is a risk that participants will be fully informed of during the IRB-approved recruitment procedures. To mitigate this risk, focus group facilitators will reinforce to participants to refrain from sharing something they feel uncomfortable with others hearing. Participants will also be reminded that part of participating in focus groups is the agreement that information shared within the group is confidential and not to be spoken of outside the group. If a participant does not feel she can maintain that agreement she will be asked not to participate.

536
537
538
539
540
541
542
543
544
545
546
547
548
549
550
551
552
553
554
555
556
557
558
559
560
561
562
563
564
565
566
567
568
569
570
571
572
573
574
575
576
577
578
579
580
581
582
583
584
585
586
587
For the Intervention Pilot Test: The lactation specialist who will be providing personalized lactation support will be trained on the protection of human subjects including maintaining privacy and handling personally identifiable information. The financial administrators facilitating the UCTs will also be trained and they will only be given the information about participants necessary for administering the monthly UCTs. A potential risk of the cash transfer is women could experience negative feelings including stress, anxiety or sadness if they are asked to or forced to share some or all of the money with their partners or others in their household/ community. We will assure women that no information about the monthly UCTs will be disclosed to anyone outside our study team. In addition, if women do not have access to a telephone of their own, we will provide them with a telephone for use to ensure to the extent possible the money will be privately and directly available to them. We will also monitor closely including via monthly follow-up phone calls with participants to promptly identify and address any adverse events experienced by women related to the monthly UCTs. Cash transfers have been used widely in a variety of settings to include similar sums of money without negative consequences to recipients. We will also discuss the progress of our study regularly with clinic staff at our research sites to identify any real or potential negative impact related to the intervention. To reduce risk of any negative interaction between our intervention and control arms we will be using two separate, but matched, clinics. In this way we attempt to avoid a potential situation where women in the control group discuss their participation in the study with women in the intervention group and vice versa leading to the control group to feel negatively about the study or members of the intervention group as they are not receiving the same supportive intervention.

Planned procedure for reporting of adverse events: All serious adverse events associated with the procedures of this study will be reported within 10 days to the appropriate IRBs. Current guidance on adverse event reporting has focused on clinical trials of drugs or devices and has not provided clear guidance on behavioral prevention trials. The primary risk to subjects in this study is loss of confidentiality. If serious or unexpected adverse events occur, these will be filed with the appropriate IRBs within ten working days. We will ask study participants to return to the research field site in the case of ongoing adverse events. We will also provide participants with a palm card containing information on how to contact the local field staff to report such incidents as HIV-related disruption of families, acts of discrimination, physical harm, adverse events following phlebotomy, or personal distress. Field staff will be trained to complete descriptions of adverse events that will then be sent electronically to the study PIs.

(a2) Potential benefits of the proposed research to the subjects and others

Participants in the study will be able to access the results of the study. The research findings have the potential to ultimately benefit other perinatal women in Kenya and elsewhere in sub-Saharan Africa who are struggling with the overlapping epidemics of food insecurity, mental health and HIV. In view of the minimal risks to subjects, and the many actual and anticipated potential benefits to research subjects and others in their community, we believe that the benefits strongly outweigh the risks. The receipt of unconditional cash transfers may provide considerable benefit to participants in meeting basic needs for themselves and their dependents during a period of time while perinatal women are typically out of the workforce. In addition, the lactation support may have direct and immediate benefit to breastfeeding women who are also confronting food insecurity, breast health concerns and other complexities that may challenge their ability to exclusively breastfeed.

The research will not provide any direct benefits to the participants, other than possible psychological benefits associated with sharing their insights and stories. As a token of appreciation, participants in the in-depth interviews and focus group discussions will be compensated for their time with up to 800 Kenyan Shillings (equivalent to ~\$8) per interview or group discussion.

(a3) Informed Consent

Research will be conducted according to Good Clinical Practice guidelines, the U.S. Code of Federal Regulations (CFR) Title 21 CFR (Part 50 – Protection of Human Subjects and Part 56 – Institutional Review Boards), and the Declaration of Helsinki. This protocol has been approved by UCSF’s Committee on Human Research (letter attached). The informed consent of each participant will be obtained before protocol-specified procedures are carried out.

The consent process will be conducted with a staff member fluent in English, Swahili and Dholou who has been trained in research ethics and the specific consenting protocol for this study. The consent process will be conducted in the language of the participants choosing. The informed consent process will highlight the specific risks associated with the study, including discomfort from in-depth discussions of HIV infection, perinatal depression and mother-to-

588 child transmission of HIV and risks for breaches to confidentiality. The participants will be informed about the
589 precautions put in place to minimize the risk of breaches in confidentiality. The participants will be informed about
590 all procedures put in place to reduce the risk of breaches in confidentiality including: the use of a unique participant
591 ID number on all research data and that her name will not be used in relation to her data and that all data will be
592 kept in a safe, locked filing cabinet or password-protected computer in a locked office. It will also be noted that
593 study staff are not practicing doctors, nurses or any type of healthcare provider and, thus, cannot diagnose, treat or
594 prescribe medications of any kind. The participant will be allowed to ask questions and the staff member will probe
595 for complete understanding during key points of the consent form. The participant can take as much time as they
596 need to make a decision and she will be reminded that she can de-enroll in the study at any time and that
597 participation is completely voluntary and will not impact her regular clinic visits. All participants will be provided the
598 contact numbers of the PI [name], [name] and the KEMRI IRB chairs to answer any questions that the
599 participant might have about the study or one's rights as a human subject. Completed, signed consent forms will be
600 kept in a locked filing cabinet in our secured research office. The participant will be allowed to take a copy of the
601 consent form home to have a reference, but will be reminded that someone finding the form may result in a breach
602 of confidentiality.

603 We have developed a separate informed consent for intervention and control participants based on previously
604 established protocols for conducting research when an intervention involves cash transfers. This will ensure the
605 participants in each arm are not influenced by the other. Given cash transfers need to be handled with care because
606 they provide financial assistance to a vulnerable population these additional steps are critical for protecting human
607 subjects.

608 **(a4) Method of maintaining confidentiality of information obtained during the study:**

609 To ensure confidentiality of participation, all data will be coded by a unique participant identifier number. Data will
610 be kept in locked cabinets and will only be provided to a subject's clinician upon the written request of the subject.
611 Research records will be kept confidential to the level allowed by law. For interview data, survey data and any
612 participant data recorded by our lactation specialist collected as part of the study, subjects will be assigned a unique
613 study identification number. Interviewers and support staff including the lactation specialist and financial
614 administrator assisting with cash transfers will be trained on procedures for maintaining privacy and will sign a
615 pledge of confidentiality. Additionally, discussion group participants will be asked to pledge that they will not share
616 the personal information of others, disclosed in the session, with anyone outside of the group. All transcripts and
617 computer records will be password-protected to prohibit illicit access. All personal identifiers will be removed from
618 any paper or electronic study forms, which will be coded only by numerical identifiers. When these procedures are
619 followed, it is highly unlikely that any information revealed by participants during the course of the interviews or
620 clinic visits will be disclosed to anyone outside the research team.

621 Primary responsibility for data and safety monitoring will fall on the PIs (Drs. [name] and [name]). In this research, the
622 primary risk to subjects is loss of confidentiality. Risks to participants will be minimized through informed consent
623 and strict confidentiality. In the case of any serious adverse events, we will ask subjects to return to the research
624 field site. We will also provide subjects with an informed consent translated into the local language of their choice,
625 so that they have the opportunity to contact the local field staff or one of the study investigators at any time. Study
626 staff will be trained to complete descriptions of adverse events that will be sent electronically to the principal
627 investigators (Drs. [name] and [name]). Serious or unexpected AEs will be reported to the appropriate IRBs within 10
628 working days of awareness of the incident.

629
630 (a5) Not applicable.

631
632 (b) Animal subjects

633 Not applicable.

635 12. EXPECTED APPLICATION OF RESULTS

636 This study will fill key gaps about the interplay of FI and perinatal depression and its impact on adherence to
637 PMTCT strategies among women living with HIV, specifically during the transition period from pregnancy to
638 postpartum. Background literature suggests there is causal, additive impact between FI and perinatal depression on
639 ART adherence and exclusive breastfeeding, however, how impactful this relationship may be and at what point
640 during the perinatal period these factors are most detrimental is not known. Furthermore, both FI and perinatal
641 depression are substantial maternal and infant health issues in their own right. Addressing them together through a
642 multi-level intervention designed to promote adherence to PMTCT strategies will have the added benefit of
643 improving overall health.

644 These efforts are aimed to help impact Sustainable Development Goals: 1) improve maternal and infant health
645 and 2) further several top Sustainable Development Goals (SDG) including SDG 1 (zero poverty), SDG 2 (zero hunger),
646 SDG 3 (good health and wellbeing), and SDG 5 (gender equality).
647

13. References

1. UNAIDS. GLOBAL AIDS UP DATE 2016. June 2016:1-16.
3. The INSIGHT START Study Group. Initiation of Antiretroviral Therapy in Early Asymptomatic HIV Infection. *The New England journal of medicine*. 2015;373(9):795-807. doi:10.1056/NEJMoa1506816.

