340 Women in this arm of the study will meet with a lactation consultant at 5 timepoints throughout the intervention: once during pregnancy and at 2-weeks, 4-weeks, 6-weeks and 3-months postpartum. During pregnancy, the lactation specialist will assess women's knowledge and experience with regards to breastfeeding and provide them information and support for optimal infant feeding after birth while emphasizing exclusive breastfeeding. Each post-partum visit with the lactation specialist will be individualized and continue to focus on optimizing infant feeding with a focus on exclusive breastfeeding for up to 6-months postpartum. During the postpartum sessions, the lactation specialist will assess for milk sufficiency or any other barriers to optimal infant feeding. The assessment will include the infant's weight and a physical assessment of women's breasts and breastfeeding practice. The lactation specialist will counsel women on how to address both perceived and actual milk insufficiency as well as address any of the other barriers to infant feeding as appropriate. Counseling topics will include women's breastfeeding timing and technique, diet, hydration and infant hunger and satiety cues to optimize safe infant feeding. Other treatments may include warm or cold compresses or the use of a breast pump to treat engorged breasts. The lactation specialist will not prescribe women any medications. Any medications the lactations specialist would recommend (for example an antibiotic to treat mastitis) will be recommended to the participant's primary perinatal care provider for further consideration and prescribing as appropriate. At the last visit (3-months postpartum) the lactation specialist will provide women with support and information about when and how to introduce affordable nutritious supplemental foods to their infants while at the same time promoting continued breastfeeding for 24-months or beyond.

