396 care for the participant and her infant (see also Table 3). At each research encounter, participants in both the
397 intervention and control groups will be reimbursed for their transportation costs and provided with refreshments.
398

399 For participants in the intervention group, the lactation specialist will coordinate to meet women, whenever
400 possible, on the same day of their research encounters with our Research Associate who will collect survey data and
401 infant weights. To the extent possible, we will also arrange the research encounters to coincide with participants
402 regular clinic visits. Following each session with participants, the lactation specialist will write or dictate a summary
403 note to include her professional assessment with regards to the adequacy of the participants milk supply, her
404 assessment of the woman's breastfeeding practices (i.e. to what extent women are exclusively breastfeeding and/or
405 any successes or challenges women experience), and a summary of the counseling or treatment she provided.

406 Women from the intervention group will also be asked to participate in exit interviews, conducted at around
407 6-months postpartum, to assess the acceptability of all intervention components and to seek suggestions for
408 improvement. An interview guide for the follow up interviews has been submitted for IRB approval along with this
409 updated protocol.

410 Table 3

	Baseline: recruitment	Birth: no face-to-face encounter	2-weeks	4-weeks	6-weeks	3-months	6-months
Demographic and Individual item Questions							
Baseline questionnaire	x						
Breastfeeding focused follow-up questionnaire		x	x		x		
6-week follow-up questionnaire					x		
6-month follow-up questionnaire V 1.1							x
SCALES							
Mental Health: PHQ-9; Perceived stress scale	x				x		x
Food Insecurity: Household food insecurity access scale	x				x		x
Financial status: Wealth Index	x				x		x
Relationships: Couples Satisfaction Index	x				x		x
Breastfeeding: Prenatal BF Self-Efficacy (pre) Postpartum Breastfeeding Self Efficacy (PP)	x(pre)		X (PP)	X (PP)	X (PP)	X (PP)	X (PP)
Social support: The Duke-UNC Functional Social Support (DUFSSQ)	x				x		x
Empowerment: Demographic Health Survey Household decision making and IPV	x				x		x
HIV related stigma: 12-item HIV stigma scale	x				x		x

411	Infant weight measured by RAs		x	x	x	x	x
412	From participant's clinical record: hemoglobin, Viral Load	x				x	x

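### The protocol's consent text says, without limit by role, phase or arm, that study staff cannot diagnose or treat, which conflicts with the lactation specialist's work in the pilot

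*Protocol*

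**What the plan says.** **Consent process (Section 11(a3)).** Among the things to be noted to participants is that "study staff are not practicing doctors, nurses or any type of healthcare provider and, thus, cannot diagnose, treat or" prescribe medications. The sentence is not confined to Phase One, to either pilot arm or to any category of staff. The end of the same section says that separate consents were developed for intervention and control participants.

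**Intervention arm (Section 8, Intervention Pilot Test, (d)(i)).** The lactation specialist meets each woman once in pregnancy and at 2, 4 and 6 weeks and 3 months postpartum. For the postpartum sessions, "The assessment will include the infant's weight and a physical assessment of women's breasts and breastfeeding practice". She counsels on low milk supply, whether real or only perceived, and "Other treatments may include warm or cold compresses or the use of a breast pump to treat engorged breasts". On medication: "The lactation specialist will not prescribe women any medications". Anything she would recommend goes to the woman's primary perinatal care provider.

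**Her records (Section 8, Intervention Pilot Test, (d)(ii)).** After each session she writes or dictates a summary "note to include her professional assessment with regards to the adequacy of the participants milk supply, her" view of breastfeeding practice, and "a summary of the counseling or treatment she provided".

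**Her status (Section 11(a4)).** The confidentiality text refers to "Interviewers and support staff including the lactation specialist and financial" administrator as people to be trained in privacy and to sign a pledge.

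**Suicidal thoughts (Section 11(a1), paragraph on the in-depth interviews).** If these are found, "we will ask participants to speak with one of our study health providers who can further screen them" and refer them.

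**The concern.** The consent section is an operative instruction: it fixes what a woman hears before she agrees. Followed literally in the intervention arm, it tells her that nobody on the study is a healthcare provider or can treat her. She then meets a specialist, supplied by the study, who examines her breasts and may treat engorgement.

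Two things are at stake. One is the accuracy of the disclosure about physical contact and care. The other is whether a woman with a breast problem understands what the specialist will handle and what is passed to her own provider. No estimate, error rate or sample size depends on this. It is a matter of consent and internal consistency.

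**Working it through.** No figure in the plan bears on the point, so the check is to set the texts side by side, one element of the consent sentence at a time.

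1. **Cannot treat.** Section 8 uses the word treatment for compresses or a pump given for engorgement, and again for what the specialist's note must record. The Phase Two analysis text in Section 9(b) also plans to identify the treatments offered. This is a direct conflict in the protocol's own vocabulary.

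2. **Cannot diagnose.** Section 8 has her examine the breasts, assess whether milk is sufficient and record a professional assessment. The protocol does not call this diagnosis, so the conflict is one of substance rather than of words, and weaker than in item 1.

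3. **Not any type of healthcare provider.** The protocol describes her as skilled and experienced but does not state her professional registration, so her formal status cannot be settled from it. The phrase does conflict with the study health providers named in Section 11(a1), but that text sits in the paragraph on the in-depth interviews, which belong to Phase One.

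4. **Cannot prescribe.** Section 8 says the same of the lactation specialist. There is no conflict.

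5. **Is she study staff?** Section 11(a4) places her with support staff. Section 11(a3) does not define study staff and does not exclude her.

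6. **Does the pilot contain a suicidality step?** The pilot paragraph of Section 11(a1) covers privacy, risks of the cash transfers, monthly calls and the use of two clinics. It has no such step. Table 3 schedules the PHQ-9 at baseline, 6 weeks and 6 months, again without one.

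**Number affected.** Consent is described as one process per woman before study procedures, and the intervention arm has 20 women:

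20 women × 1 consent process = 20 at most.

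The breast assessments number 20 women × 4 postpartum sessions = 80 as planned. That figure counts sessions, not misinformed consents, and treatment for engorgement is conditional within them. It is not the measure of this point.

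**The case against.** **Study staff may mean only research assistants and interviewers.** The person taking consent is called a staff member, the lactation specialist is usually named by her role, and Section 11(a4) groups her with support staff only for privacy training. This reading is possible. But the protocol does not state it, and a participant hearing the sentence has no reason to exclude the specialist the study provides.

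**Treat may refer only to medications.** The sentence ends with medications, but diagnose cannot take that object, and the premise about healthcare providers is wider than prescribing. This defence does not remove the conflict.

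**The intervention-arm consent may already be right.** This stands. Separate consents exist and are not shown. A reader might infer that the intervention form is false, but the documents do not support going that far. Only the protocol's description of the process can be criticised. The stated grounds for separate consents are the handling of cash transfers and keeping the arms from influencing each other, so they do not show that the specialist's role was clarified either.

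**The referral route is stated.** This also stands in part. Section 8 passes medication recommendations, with mastitis as the example, to the woman's own provider. That softens the safety concern but leaves the conflict over treatment.

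**Suicidality screening in the pilot.** Because the PHQ-9 is used there, a reader might infer that study health providers also screen pilot participants and that the consent sentence is wrong for the intervention arm on that ground too. The text places that step only in the in-depth interview procedures, so the inference is unsupported.

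**Conclusion.** The point holds as a contradiction within the protocol. The unrestricted consent statement conflicts with the lactation specialist's described work, most clearly on treating. It conflicts separately with the study health providers in the Phase One interview procedures. The prescribing part is consistent.

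At most 20 intervention-arm consent processes are affected. This assumes that the Section 11(a3) description is applied to the pilot as written and that study staff includes the lactation specialist, as Section 11(a4) suggests. Whether the intervention-arm form carries the sentence is unknown. The point deserves correction because the text governs disclosure to participants and is easily put right.

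**What to change.** Reconcile the consent text in Section 11(a3) with the pilot procedures in Section 8 ((d)(i) and (d)(ii)), the in-depth interview paragraph of Section 11(a1) and the staff listing in Section 11(a4). Make the statement role-specific: name the roles to which the bar on diagnosing and treating applies, and cover the lactation specialist and the study health providers separately. The sponsor decides each role's scope.

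Then check that the intervention-arm consent describes what the lactation specialist does and does not do, and to whom she refers, as Section 8 states it.

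The cost is protocol wording, plus an IRB amendment if the form carries the sentence. No visit, procedure or analysis changes.
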